5.6 Follow-up Post Surgery Visit

- 5.6.1 Adverse events will be collected through the post-surgery follow-up visit and all related or possibly related adverse events for at least 30 days following the last dose of LEAG and continue to be followed until all adverse events have resolved or stabilized (Grade 2 or less by CTCAE vs. 3.0).
- 5.6.2 Obtain vital signs and perform physical exam.
- 5.6.3 Performance status will be completed.
- 5.6.4 Duration of follow up

Patients will be followed until the post-surgery follow-up visit (generally 10-20 days) following surgical resection. All related or possibly related adverse events will be followed for 30 days from the final dose of LEAG or until resolution or stabilization (Grade 2 or less) of adverse event. Patients removed from study for unacceptable adverse events will be followed until resolution or stabilization of the adverse event.

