	Evaluate changes in inflammatory mediator proteinomic panel (adiponectin, CRP, HGF, IGF-1, IGF-1R, IL-10, IL-12p40, IL-1b, IL-1ra, IL-2, IL-23, IL-4, IL-6, IL-8MCP-1, TGFb1, TNFa).
	Establish a comparison of biomarkers between breast cancer patients and the database of women with increased breast cancer risk in the SELF study.
	Collect anthropometric data (height, weight, body composition, waist-hip ratio), dietary history, exercise habits, insulin resistance blood panel (HOMA index, leptin, ghrelin, and adiponectin) and Gail Score.
Hypothesis	LEAG will have an anti-proliferative effect on human breast tumors and benign breast epithelia. LEAG may favorably alter biomarkers of inflammation and the metabolic syndrome.
Safety Considerations	All patients will be monitored for toxicity related to therapy. Adverse events will be collected through the post-surgery visit and all related or possibly related adverse events for 30 days following discontinuation of LEAG therapy or until resolution or stabilization of the adverse event. Discontinuation of treatment will be considered in patients experiencing excessive toxicity.
Statistical Considerations	High variability among tumors in the patient population is anticipated. Each patient will serve as her own control; pre-treatment biopsy tissue will be compared to post-treatment surgical tissue. Descriptive statistics including the mean, median, range, standard deviation, interquartile range, skewness, and kurtosis will be calculated for each measure. Paired t-tests, or Wilcoxon signed-rank tests, depending on the distributional characteristics of the variables, will be used to assess changes in biomarkers from biopsy to surgery. In order to examine the inter-relationships between the anthropometric data, the cytological markers, serum ginsenoside concentrations, and a panel of inflammatory serum proteins, data visualization techniques will be employed. Correlation coefficients will be used to summarize linear relationships between continuous measures. Regression techniques will be used to model nonlinear relationships. All statistical procedures will be performed in consultation with the Division of Statistics and Research Consulting at SIU School of Medicine.

Timeline	Patient enrollment and data collection are expected to be complete within 72 months.
-----------------	--

TABLE OF CONTENTS

	Page
SYNOPSIS	i
SCHEMA	vii
1.0 OBJECTIVES	1
1.1 Primary Objectives	1
1.2 Secondary Objectives	1
2.0 BACKGROUND	2

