5.7.3 Added post-LEAG but pre-surgical laboratory test

- Repeat Platelet Function Assay-100 test prior to surgery (2 citrate tubes of blood drawn day of surgery)

5.7.4 Interim Analysis of Platelet Function Assay completed following completion of 5 subjects. All PFA-100 results were within normal limits. Recommendations from Data Review Team state that further Platelet Function Assay testing is not necessary.

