11.2 Adverse Event (AE) Reporting

An adverse event is any untoward medical occurrence in a patient that does not necessarily have

a causal relationship with the study intervention. An AE can, therefore, be any unfavorable and unintended sign (including an abnormal laboratory finding), symptom or disease temporarily associated with the use of a medical treatment or procedure (attribution of unrelated, unlikely, possible, probable, or definite).

Adverse events will be reported once treatment with the study agent begins to the Chairperson of the Springfield Committee for Research Involving Human Subjects (SCRIHS) at Southern Illinois University School of Medicine, [name], [contact].

Submission requirements of AE's, as defined by the SCRIHS procedure manual, will be strictly adhered to.

Adverse events that are expected and outlined in the pre-op discussion and/or listed in the surgical consent as related to surgery or anesthesia will not be reported.

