With respect to the safety goals of this study, toxicities specific to this therapy are not known at this time. Therefore, patients will be monitored for unexpected toxicities and if any serious side effects are observed, an independent monitoring committee will examine the data and evaluate the appropriate course of the study. At the conclusion of the study, all unexpected toxicities will be summarized and reported.

To evaluate a potential effect of LEAG on platelet function, a Platelet Function Assay-100 test will be conducted on the first five patients enrolled. Platelet function will be assessed prior to LEAG administration and prior to surgery on the day of surgery. All adverse events will be

monitored for 30 days beyond the last dose of LEAG, including bleeding complications. Following completion of the study protocol by 5 patients the Data Safety Monitoring Committee will review the adverse events associated with LEAG administration paying particular attention to platelet function. The committee will make a recommendation on continued monitoring of platelet function or its removal from required study procedures for the remainder of patients enrolled. – See section 5.7.4

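### The adverse event follow-up rules conflict, and typically 9-19 of the 30 days after the last dose have no scheduled contact at which new events would be ascertained

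*Combined protocol and SAP*

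**What the plan says.** Four places in the protocol say how long adverse events are followed.

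- **Section 5.6.1.** All adverse events are collected up to the post-surgery visit. Related or possibly related ones are collected "for at least 30 days following the last dose of LEAG and continue to be followed until all adverse events have resolved or stabilized", with stabilization defined as Grade 2 or less.
- **Section 5.6.4.** Related or possibly related events are "followed for 30 days from the final dose of LEAG or until resolution or stabilization (Grade 2 or less) of adverse event". The same section gives the timing of the last visit: "Patients will be followed until the post-surgery follow-up visit (generally 10-20 days) following surgical resection". Its closing sentence requires follow-up to resolution or stabilization for patients taken off study because of unacceptable events.
- **Synopsis, Safety Considerations.** Related or possibly related events are collected "for 30 days following discontinuation of LEAG therapy or until resolution or stabilization of the adverse event", without the Grade 2 definition.
- **Section 14.7, Analysis of Safety.** All adverse events are to be "monitored for 30 days beyond the last dose of LEAG, including bleeding complications". This sentence stands in the paragraph on platelet testing in the first five patients.

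On contacts, Section 5.4 provides one telephone call, 48-72 hours after LEAG is started. The calendar in Section 12.0 has no column after Study Visit Three, which is the post-surgery visit. Section 7.2 ends concomitant medication monitoring at that visit too. Section 5.3.1 places the final dose on the day before surgery.

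**The concern.** Two things do not fit together. First, 5.6.1 joins the 30 days and the resolution criterion with *and*, while 5.6.4 and the synopsis join them with *or* and do not say which governs. Staff who follow different sections could close the same event at different times. Second, the 30-day duty has no visit or call behind it once the post-surgery visit has taken place.

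What is at stake is the completeness of late safety data. A related event still open at day 30 could be closed unresolved. A new event between the visit and day 30 might be recorded for one patient and not for another, depending on whether anyone happened to be in touch with her. The expedited reports in Section 11.3 do not help, because their clocks start only when the sponsor-investigator learns of the event. Restricting late collection to related events does not help either, because attribution can be judged only once an event is known.

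**Working it through.** **Rules set side by side**

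| Case | 5.6.1 | 5.6.4 and synopsis, read literally | 14.7, if general |
|---|---|---|---|
| Related Grade 3 event, open at day 30, patient completed dosing | Follow until resolved or stabilized | May stop at day 30 | 30 days; no resolution rule given |
| New bleed on day 25, after the visit, judged unrelated | Not covered | Not covered | Covered |

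The first row is a direct conflict, since the closing sentence of 5.6.4 protects only patients removed from the study for adverse events. The second row is a conflict only if 14.7 applies beyond the first five patients.

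**Days without a scheduled contact**

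Inputs:
- Last dose: *k* days before surgery, with *k* = 1 for a patient who completes dosing (5.3.1).
- Post-surgery visit: *v* days after surgery, generally 10-20 (5.6.4).
- Window: 30 days after the last dose (5.6.1, 5.6.4, synopsis, 14.7).

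Formulas: visit day after last dose = *k* + *v*; uncovered days = max(0, 30 - *k* - *v*).

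Patient who completes dosing (*k* = 1):
- Earliest usual visit: 1 + 10 = day 11; uncovered 30 - 11 = 19 days; 19/30 = 63% of the window.
- Latest usual visit: 1 + 20 = day 21; uncovered 30 - 21 = 9 days; 9/30 = 30% of the window.
- To reach day 30, the visit would have to fall 30 - 1 = 29 days after surgery, which is 29 - 20 = 9 days beyond the usual upper end.

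Early stopping shortens the gap, because the last dose moves back while surgery and the visit are taken to stay in place:

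| Last dose | *k* | Visit, days after last dose | Uncovered days |
|---|---|---|---|
| Day before surgery | 1 | 11-21 | 9-19 |
| First of a planned 5 doses | 5 | 15-25 | 5-15 |
| First of a planned 14 doses | 14 | 24-34 | 0-6 |

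The protocol states no figure for this gap, so there is none to reproduce. A contact at day 30 brings the uncovered days to 0 in every row.

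**The case against.** The best defense is that 5.6.1 already states the full rule, and that 5.6.4 and the synopsis merely abbreviate it. The two subsections stand close together, and a careful coordinator would probably apply the stricter one. That is a fair reading, but the text does not say which subsection governs, and the synopsis carries only the looser wording. The conflict is therefore real, though small.

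The second defense concerns 14.7. Its sentence sits among statements about the roll-out patients, and the paragraph ends by pointing to 5.7.4, which records that review as complete: "All PFA-100 results were within normal limits". A reader might infer that 14.7 sets a firm third rule for everyone. The documents do not settle that. The sentence is not expressly limited to the five patients, but its context favors them. Nor does 5.7.4 close the question of late bleeding. It ends platelet testing without mentioning the 30-day monitoring, and the five patients reviewed were barred from aspirin and other anticoagulants (5.7.1), a bar that 7.3.4 confines to them.

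A reader might also infer that nothing is collected after the visit. That is wrong: 5.6.1 plans collection of related events to at least day 30, and 14.7 plans monitoring to day 30. What is missing is a scheduled contact. Even this has a limit, because the study schema and the consent pages are not readable in the copy examined, so a contact or patient instruction given only there cannot be excluded.

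Section 11.2 says that expected events "listed in the surgical consent as related to surgery or anesthesia will not be reported". This concerns reporting to the review board and does not decide what is collected.

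**Conclusion.** The point holds in a limited form. The *and/or* conflict between 5.6.1 and 5.6.4 with the synopsis is plain on the text. For a patient who takes the last dose the day before surgery, about 9-19 of the 30 days (30%-63% of the window) have no scheduled contact at which new events would be ascertained. The general scope of 14.7 is arguable, and the conclusion does not depend on it.

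The range assumes a visit 10-20 days after surgery. The protocol calls this general rather than fixed, so the figures are typical and not bounds. They are shares of calendar days. A reader might take them as the share of events missed, but the documents give no event counts, and late events may be few.

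The consequence is modest. Events up to the visit are collected under every version of the rule. The plan defines no 30-day event rate, promising only that "all unexpected toxicities will be summarized and reported", and no biomarker objective is affected. This is an inexpensive improvement to consider, not a flaw that threatens the trial's conclusions.

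**What to change.** 1. **Synopsis and 5.6.4.** State that related or possibly related events are followed until 30 days after the final dose or until resolution or stabilization (Grade 2 or less), whichever is later. This brings both into line with 5.6.1.
2. **Section 12.0.** Add one telephone call at day 30 after the final dose to ascertain new events, including bleeding.
3. **Section 14.7.** Either limit the 30-day all-event sentence to the roll-out patients, or state that all new events are recorded to day 30 and only related or possibly related ones are followed to resolution. The rule in item 1 should not simply be copied into 14.7, because it would then require unrelated surgical events to be followed to resolution.

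The cost is a few aligned sentences, one calendar entry, 25-50 short calls (the planned accrual in Section 16.1), and some late unrelated events recorded.

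The version history shows that version 1.8 (2018) revised the objectives according to which data were available, so follow-up may already be over. In that case, report each patient's days from last dose to last adverse event contact. For patients without a contact at day 30 or later, describe safety results as running through the post-surgery visit. That costs one derived variable and one line in the safety summary.

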5.7 Study Role-Out: Additional Procedures for the First 5 Patients

Additional procedures will be conducted to evaluate the effects of LEAG on platelet function. The first 5 patients enrolled will have platelet function assessed prior to surgery with an interim analysis of platelet function and bleeding complications prior to additional patient enrollment to determine if platelet function should be evaluated in all study patients. After 5 patients have completed the study protocol a safety meeting will convene to determine if pre-operative assessment of platelet function is needed in all study patients. The following procedures have been added for the first five patients.

- 5.7.1 Added Exclusion Criteria
 - Role-out patients taking aspirin, other anti-coagulants, or anti-platelet aggregate are excluded at this time. Platelet Function Assay -100 may be affected by anti-coagulant use.

5.7.2 Added Pre-LEAG Administration Laboratory Test

- Platelet Function Assay-100 test (2 citrate tubes of blood prior to taking LEAG)

5.7.3 Added post-LEAG but pre-surgical laboratory test

- Repeat Platelet Function Assay-100 test prior to surgery (2 citrate tubes of blood drawn day of surgery)

5.7.4 Interim Analysis of Platelet Function Assay completed following completion of 5 subjects. All PFA-100 results were within normal limits. Recommendations from Data Review Team state that further Platelet Function Assay testing is not necessary.

6.0 GINSENG THERAPY

6.1 Summary

- LEAG, 1 gram (4 capsules) by mouth daily taken with food in the morning.
- All patients will receive a minimum of 5 days and a maximum of 14 days of treatment with LEAG for treatment prior to surgical therapy.
- The final dose of LEAG will be taken the day prior to surgery to satisfy the fasting recommendation prior to surgery.

6.2 Study Agent

The investigational agent is a clear gelatin capsule containing 250 mg of lyophilized water-extract of American Ginseng root. The lyophilized extract is a white powdery substance that can be seen through the clear gelatin capsule. The capsule is intended for oral use and does not contain any active or inactive substances other than the lyophilized water-extract of American Ginseng root. For additional information on general use of all types of ginseng, please see the Customized Monograph published by Clinical Pharmacology (Appendix G) and the Investigator's Brochure.

6.3 Preparation

No preparation needed.

6.4 Mechanism of Action

The major active components of ginseng are the ginsenosides found within the compound. Ginsenosides, also called panaxosides, are triterpenoid saponin glycosides. Asian ginseng contains up to 13 different ginsenosides which may have opposing actions on one another. Small animal tests have indicated that the active components of ginseng can prolong exercise time,

stimulate protein synthesis, inhibit platelet aggregation, stimulate the proliferation of hepatic ribosomes, prevent stress-induced ulcers, and increase the activity of interferons (clinical pharmacology). The antiplatelet effect appears to be a result of the activity of panaxynol and ginsenosides Ro, Rg1, and Rg2. Enhanced nitric oxide production in the lung, heart, and kidney, as well as the corpus cavernosum has been proposed as a mechanism of action. Various glycans have demonstrated a hypoglycemic effect in normal mice (clinical pharmacology). The ginsenosides found within the gelatin encapsulated lyophilized water-extract of American Ginseng root used in this study are as follows:

Ginsenosides per gram of Gelatin Encapsulated lyophilized water-extract of American Ginseng Root

Ginsenoside	mg
Rg1	2.38
Re	16.3
Rf	0
Rb1	25
Rc	4.60
Rb2	0.81
Rd	7.75
Total	40.04

6.5 Administration Guidelines

Patients will be instructed verbally on the administration of gelatin encapsulated lyophilized water-extract of American Ginseng root.

The study agent will be self-administered in an open-label, unblinded manner to all patients enrolled in the study. During the treatment period, patients will receive 1 gram (4 capsules) of LEAG each day. Capsules should be taken at approximately the same time daily. To reduce the insomnia and hypoglycemic effects, LEAG administration is recommended with breakfast.

Patient must complete at least 5 days of treatment with LEAG prior to day of surgery. LEAG will be dispensed to the patient on the last clinic visit prior to the scheduled date of surgery. Treatment with study medication will be initiated 5 to 14 days prior to surgery and end the night before surgery. **If the patient is not seen in clinic the day that study drug is to be initiated, a reminder telephone call will be made to the patient.** A capsule count will be taken the day of surgery.

Patients will be given a drug diary to record dates of ginseng therapy in order to monitor compliance.

6.6 Duration of Therapy

In the absence of treatment delays due to adverse event(s), treatment may continue for 14 days or until one of the following criteria applies:

- Intercurrent illness that prevents further administration of treatment,
- Unacceptable adverse event(s) or toxicity of grade 3 or higher,
- Patient decides to withdraw from the study, or
- General or specific changes in the patient's condition that render the patient unacceptable for further treatment in the judgment of the investigator.

6.7 Dose Reductions

Reported adverse events and potential risks are described in Section 7. If LEAG therapy is discontinued prior to surgery, blood levels of LEAG will not be drawn on the day of surgery but the breast tissue will be studied for immunohistochemistry, in situ TUNEL, and oxidative stress as described. Dose reductions of LEAG are not permitted.

6.8 Storage and Accountability

All study material should be stored at room temperature and out of direct light. LEAG will be supplied to the patients in white opaque bottles with child resistant closures. The study agent required for completion of this study has been provided by [name] laboratory at Southern Illinois University. The Clinical Research Office will document receipt and dispensation of study agent on the accountability log (Appendix H) in accordance with regulations.

Agent Inventory Records – The investigator, or a responsible party designated by the investigator, must maintain a careful record of the inventory and disposition of the American Ginseng. Dispensation of drug to each individual patient must be recorded on the accountability log (Appendix H).

6.9 Availability

The American Ginseng root has been obtained from the Ginseng Board of Wisconsin and analyzed for content by consumerlab.com. The extraction process was performed by [name] at Southern Illinois University prior to analysis. American Ginseng will only be available through the Clinical Research Office of the Simmons Cancer Institute at SIU

School of Medicine. The investigational agent will be stored at room temperature in a locked cabinet.

7.0 Risks/ Precautions

7.1 Contraindications/Precautions

- Ginseng is generally well tolerated when taken orally. Various sources indicate that long term use should be limited to 3 months.
- The most common side effects reported include headache, nervousness/anxiety, sleep disturbances, and gastrointestinal disturbances.
- Estrogenic effects, such as breast tenderness and vaginal bleeding have been reported though not well substantiated.
- Reports of changes in blood pressure and blood sugar levels indicate that individuals being treated for hypertension and/or diabetes should use ginseng with caution.
- Ginseng has been reported to interact with coumadin. Use with coumadin should be closely monitored.

7.2 Concomitant Medications

Because there is a potential for interaction of American Ginseng with other concomitantly administered drugs, the case report form must capture the concurrent use of all other drugs, over-the-counter medications, and alternative therapies.

All medications currently being taken by the subject (including over the counter medications and herbal supplements) need to be entered into the Concomitant Medication Log for each subject. Concomitant medications will be monitored from enrollment into the study through the post-surgery visit. The information collected will include dates of administration, dosage, and form.

7.3 Prohibited Concomitant Medications

7.3.1 Products Containing Ginseng

- All products containing or claiming to contain any form of ginseng product including oral and external application products are prohibited from use during this study and for six weeks prior to initial biopsy.

7.3.2 Coumadin

- Due to a report concerning the possible interaction between coumadin and ginseng, patients currently being treated with coumadin are ineligible for the study.

All other medications, prescription, and over the counter, that affect platelets and/or clotting functions should be used with caution.

7.3.3 Herbal Supplements and Alternative Medications not approved by the FDA.

- All Herbal Supplements and Alternative Medications not approved by the FDA including oral and external application products are prohibited from use during this study and for six weeks prior to initial biopsy.

